3.1 Registration – Inclusion Criteria

3.11 Registered to COLOMATE ACCRU-GI-1611 and:

- a) COLOMATE Companion Trial Recommendation Form indicates patient qualifies to be screened for a COLOMATE companion trial.
- b) COLOMATE Companion Trial Recommendation Form date of completion is \leq 30 days prior to randomization.

3.12 Age \geq 18 years.

3.13 Histologically and/or cytologically confirmed adenocarcinoma of the colon or rectum that is metastatic and/or unresectable.

3.14 Documented wild-type in *KRAS* and *NRAS* (codons 12, 13, 59, 61, 117, and 146) and in *BRAF* codon 600, based on tumor tissue taken from primary or metastatic site prior to receipt of anti-EGFR therapy.

3.15 Progression, intolerance, or contraindication to a fluoropyrimidine (e.g., 5-fluorouracil or capecitabine), oxaliplatin, irinotecan, an anti-VEGF monoclonal antibody (bevacizumab, ramucirumab, or afibbercept), and an anti-PD-1 monoclonal antibody (nivolumab or pembrolizumab) if tumor has deficient mismatch repair proteins (dMMR) or is microsatellite instability-high (MSI-H).

3.16 Disease progression after treatment with an anti-EGFR monoclonal antibody (cetuximab and/or panitumumab) for at least 4 months (minimum of 8 biweekly treatments or 16 weekly treatments at full or partial dose).

NOTE: Treatments do not need to be administered consecutively.

NOTE: Dose reductions or delays are permitted.

3.17 Greater than 90 days has elapsed between the most recent treatment with an anti-EGFR therapy (cetuximab or panitumumab) and blood collection for COLOMATE ACCRU-GI-1611.

3.18 At least one site of disease that is measurable by RECIST criteria (as defined in Section 11.0) that has not been previously irradiated; if the patient has had previous radiation to the target lesion(s), there must be evidence of progression since the radiation.

3.19a Life expectancy \geq 3 months per estimation of investigator.

3.19b ECOG Performance Status (PS) 0, 1, or 2. (Form is available on the ACCRU web site).

3.19c The following laboratory values obtained \leq 7 days prior to randomization.

- Absolute neutrophil count (ANC) \geq 1500/mm³ without colony stimulating factor support
- Platelet count \geq 75,000/mm³
- Hemoglobin >8.0 g/dL
- Total bilirubin \leq 1.5 x upper limit of normal (ULN)
- Aspartate transaminase (AST) \leq 2.5 x ULN (\leq 5 x ULN for subjects with liver involvement of their cancer)

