12.0 Descriptive Factors

- 12.1 ECOG PS: 0 vs. 1 vs. 2.
- 12.2 Disease characteristics: Unresectable vs. Metastatic.
- 12.3 Prior treatment: TAS-102 vs. regorafenib vs. neither.
- 12.4 Primary tumor location: cecum vs. ascending vs. hepatic flexure vs. transverse vs. splenic flexure vs. descending vs. sigmoid vs. rectosigmoid vs. rectum vs other.
- 12.5 Microsatellite instability or mismatch repair deficiency tested: Yes vs. no.
 - 12.5.1 If yes, MSI-High (MSI-H) vs. microsatellite stable/MSI-Low (MSS/MSI-L); loss of mismatch repair protein (MMR deficient, dMMR) vs. mismatch repair proteins intact (MMR proficient, pMMR).
- 12.6 *ERBB2* (HER2) amplification tested: Yes vs. no.
 - 12.6.1 If yes, *ERBB2* amplified vs. *ERBB2* equivocal vs. *ERBB2* not amplified.

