16.12 Interim Analysis

One interim analysis for futility will be conducted when at least 42 patients across both arms combined have provided documentation of death. Overall survival will be used as the endpoint for the interim analysis. The interim futility boundary was selected using EAST software. Un-stratified log-rank p-value will be used for decision making. The trial will continue accrual while the interim analysis is being conducted. If the 1-sided p-value > 0.529 for panitumumab compared to standard therapy (TAS-102 or regorafenib), which corresponds to a hazard ratio (HR) > 1.022 , the panitumumab will be considered as futile and the accrual will be suspended. Otherwise, if the 1-sided p-value ≤ 0.529 (HR ≤ 1.022), the study will continue to full accrual and the final analysis will be conducted as described below.

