16.13 Final Analysis

Efficacy analysis will be conducted when at least 83 death events, across

both arms combined, have been observed. The stratified log-rank test will be used for decision making except when there are 0 events in any of the strata; in that case, the un-stratified log-rank will be used for decision making. If the 1-sided p-value is > 0.15 for panitumumab compared to standard therapy (TAS-102 or regorafenib), which corresponds to a hazard ratio (HR) > 0.797 , panitumumab will be considered as ineffectual; if the 1-sided p-value ≤ 0.15 (equivalently, HR ≤ 0.797), panitumumab will be considered as promising for future study. All eligible patients who sign the consent form, are randomized, and received any protocol treatment are considered evaluable for this endpoint.

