16.15 Power and Sample Size

The primary goal is to compare the OS between patients who are randomized to panitumumab and those randomized to standard therapy (TAS-102 or regorafenib). The null hypothesis is that the panitumumab arm does not show a superior OS outcome compared to standard therapy (TAS-102 or regorafenib). The alternative hypothesis is that the panitumumab arm has improvement in OS compared to standard therapy (TAS-102 or regorafenib).

We will enter 53 evaluable patients to each arm of the study using a 1:1 randomization scheme (106 evaluable patients in total); unless the study is stopped early. Stratification factors are defined in section 5.0. With 53 evaluable patients per arm, we have 80% power to detect an improvement in the median OS from 6.5 to 10 months (HR=0.65), assuming a 1-sided significance level of 0.15 and an accrual rate of 8 patients per month. The trial has a single interim analysis for futility, adopting the Rho family (Rho=1.5) beta spending function for controlling the overall type II error rate and will be considered non-binding.

16.151 Operating Characteristics

The table below shows the operating characteristics assuming the OS follows the exponential survival function along with a one-sided significance level of 0.15.

The table below includes the operating characteristics according to the monitoring plan outlined above. The proportion of times that 1) the study would stop early at the interim analysis due to futility of panitumumab, and 2) the study would conclude panitumumab is superior to TAS-102 or regorafenib at the final analysis, are tabulated by true OS median survival times and equivalent true

hazard ratios for OS by treatment groups.

True median overall survival (months) ¹		True Hazard Ratio	% of times the study will be stopped for futility at the interim analysis ²	% of times that panitumumab is deemed superior at the final analysis ²
TAS-102 or regorafenib	panitumumab			
6.5	6.5	1	47.7	14.1
6.5	7.2	0.90	34.3	26.8
6.5	7.9	0.82	24.3	41.9
6.5	8.6	0.76	16.5	56.7
6.5	9.3	0.70	11.2	69.9
6.5	10	0.65	7.5	79.4

¹ Although we use the median OS to illustrate each scenario, the hypothesis testing is based on the entire survival curve.

² Proportions are based on 50,000 replicates in a simulation study

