16.51 Progression Free Survival (PFS)

Progression free survival is defined as the time from randomization to documentation of disease progression or death due to any cause, whichever is first. For patients who are progression-free and alive, PFS will be censored at the last disease evaluation. If the patient did not have any disease evaluation post randomization, PFS will be censored at one day after randomization. The distribution of progression free survival will be estimated using the method of Kaplan-Meier (Kaplan 1958). Progression free survival will be compared between the 2 treatment arms using the log-rank test.

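### Neither OS decision test uses ECOG PS; pre-specified adjustment would be a cheap gain in efficiency, but the stated 80% power is not an error

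*Combined protocol and SAP*

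**What the plan says.** - **Entry.** Section 3.1 admits "ECOG Performance Status (PS) 0, 1, or 2". The Section 4.0 test schedule has PS recorded within 28 days before randomisation.
- **Role of PS.** Its only listed use is in Section 12.0, as "ECOG PS: 0 vs. 1 vs. 2". It is not among the Section 5.0 factors, which are tumour side and prior TAS-102 or regorafenib. Section 6.21 adds registering membership for the dynamic allocation, but not PS.
- **Interim OS test (16.12, 42 deaths).** "Un-stratified log-rank p-value will be used for decision making". Futile if one-sided p > 0.529.
- **Final OS test (16.13, 83 deaths).** "The stratified log-rank test will be used for decision making", reverting to the un-stratified test if any stratum has no events. Promising if one-sided p ≤ 0.15. The section does not list the strata.
- **Power (16.15).** 80% for medians of 6.5 and 10 months (HR 0.65), "assuming a 1-sided significance level of 0.15 and an accrual rate of 8 patients per month". The table in 16.151 assumes exponential OS, names no covariate, and gives 79.4% at HR 0.65.
- **PFS (16.51).** "Progression free survival will be compared between the 2 treatment arms using the log-rank test". Nothing is said about stratification, and 16.5 makes the secondary p-values descriptive.

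**The concern.** The go/no-go decision rests on one comparison with 83 deaths. If survival differs strongly by PS, a log-rank test that ignores PS compares two mixed populations, and the hazard ratio it sees lies closer to 1 than the hazard ratio within PS levels. Power falls if the within-level effect is what the design assumed. Chance imbalance in PS between arms also goes unadjusted. What is at stake is a truly active treatment being labelled ineffectual more often than necessary, when a baseline value already on the case report form could reduce that risk.

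**Working it through.** **Inputs from the protocol.** 106 evaluable patients, 1:1; looks at 42 and 83 deaths; one-sided p cut-offs 0.529 and 0.15; control median 6.5 months; HR 0.65; 8 patients per month.

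**Step 1: reproduce the stated power.** With d deaths and 1:1 allocation, the expected log-rank Z is (√d / 2) × |ln HR|.
- Final look: (√83 / 2) × 0.4308 = 1.962. The critical value is 1.036. Power without an interim is Φ(1.962 − 1.036) = 82.3%.
- Interim: (√42 / 2) × 0.4308 = 1.396. The boundary is Z = −0.073. Chance of stopping is Φ(−0.073 − 1.396) = 7.1% (table: 7.5%).
- Both looks, bivariate normal with correlation √(42/83): 80.3% at HR 0.65 (table: 79.4%) and 14.1% at HR 1 (table: 14.1%).
- Critical hazard ratios: exp(−2 × 1.036 / √83) = 0.797, and exp(2 × 0.073 / √42) = 1.023 (protocol: 1.022).

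The plan's figures reproduce.

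**Step 2: let PS be prognostic, with HR 0.65 within each PS level.** All PS inputs are assumptions: three PS 0/1/2 splits, and a death hazard multiplied by 1.5, 2.0 or 2.5 per level. Simulation used 8,000 to 18,000 trials per scenario (Monte Carlo error about 0.3 to 0.5 points). Power in %:

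| PS split (%) | Hazard per level | Planned tests | Adjusted Cox, both looks | Log-rank, 12 strata including PS |
|---|---|---|---|---|
| 45/50/5 | ×1.5 | 77.5 | 79.2 | 75.2 |
| 45/50/5 | ×2.0 | 75.1 | 79.5 | 75.6 |
| 35/50/15 | ×1.5 | 76.4 | about 79-80 | 74.4 |
| 35/50/15 | ×2.0 | 73.4 | about 79-80 | 74.1 |
| 30/40/30 | ×1.5 | 76.4 | 79.3 | 74.2 |
| 30/40/30 | ×2.0 | 71.4 | 79.3 | 73.8 |

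At ×2.5 the planned tests gave about 66-72%. Separate runs with other assumptions for side and prior therapy put the planned tests at about 72-78% and the adjusted model at about 78-80% for ×1.5 to ×2.0.

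Cross-check: in these scenarios the marginal HR moved to about 0.66-0.69. Putting those values into Step 1 gives 78.3% at 0.66 and 72.1% at 0.69, in line with the table.

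**Step 3: take 0.65 as the marginal HR instead.** The within-level HR must then be stronger.

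| PS split (%) | Hazard per level | Within-level HR | Planned tests | Adjusted Cox |
|---|---|---|---|---|
| 35/50/15 | ×1.5 | 0.639 | 78.5 | 80.8 |
| 35/50/15 | ×2.0 | 0.618 | 79.0 | 84.3 |
| 30/40/30 | ×2.0 | 0.609 | 79.4 | 86.7 |

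**Step 4: no prognostic effect.** Planned 79.1% against adjusted 80.2% in one set of runs, 78.6% against 79.3% in another. Adjustment cost nothing.

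**Step 5: how much is due to PS?** In a run at ×1.5, power was 77.7% as planned, 78.7% for Cox with the two Section 5.0 factors only, and 79.9% with PS added. At ×2.0 it was 71.9%, 73.1% and 78.5%. About 1 point comes from the change of test; the rest is PS.

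**Step 6: type I error.** Overall, with the futility rule applied: planned 13.4-14.6%, adjusted 13.7-15.1%. For the final look alone, the Wald test gave 14.5-15.9% in one set of runs and about 15.6-17% in another (standard error about 0.7 points), so it may run slightly above 15%.

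**Step 7: interim stratification.** Stratifying the 42-death look by the two Section 5.0 factors moved overall power from 78.8% to 78.6% with no prognostic effects, and left it at 78.3% when both factors were prognostic.

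**Step 8: chance imbalance.** With 53 per arm and an assumed 15% at PS 2, the between-arm difference has a standard deviation of √(2 × 0.15 × 0.85 / 53) = 6.9 percentage points.

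**The case against.** The strongest reply is that 16.15 and its table define the effect at arm level: two medians, exponential survival and one hazard ratio between groups. Read that way, 0.65 is marginal, planned power stays at 78.5-79.4% even with a prognostic PS, and adjustment is a bonus. That stands, and it is why a reader who infers that true power is below 80% goes further than the documents allow. They do not say whether 0.65 is marginal or conditional. Nor do the medians settle it: in the simulations, medians of 6.5 and 10 months went with a within-level HR of 0.65, while a marginal HR of 0.65 implied a panitumumab median of 10.2 to 10.7 months.

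A reader might also infer that the un-stratified interim and the PFS test lower power. They do not: Step 7 shows an effect of 0.2 points or less for the interim, futility is non-binding, and PFS has no stated power. Section 16.51 is silent on stratification; it does not exclude it.

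Other parts of the reply also stand. A log-rank stratified by randomisation factors is a standard primary test. Chance PS imbalance does not invalidate it, since randomisation protects the type I error. A material loss needs a strong PS effect. The change also costs more than wording, because the cut-offs were built for the log-rank. None of this shows a disadvantage in power from adjusting.

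**Conclusion.** The point holds as an efficiency improvement worth making, not as an error in the power statement, which reproduces. The gain depends on inputs absent from the documents. With HR 0.65 within PS levels and an assumed 1.5- to 2.0-fold hazard per level, planned power is about 71-78% against about 78-80% adjusted. With 0.65 as the marginal HR, the stated power essentially stands and adjustment gives about 81-87%. No single figure for the loss can be given. The case for acting is that the direction is the same under both readings and nothing was lost when PS had no effect.

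**What to change.** - **16.13.** Base the decision on the one-sided p-value for treatment (cut-off still 0.15) from a Cox model with treatment, the two Section 5.0 factors and ECOG PS (0/1/2) as covariates. Prefer the score or likelihood-ratio test, given the possible slight excess size of the Wald test. State the factors explicitly, including whether registering membership (6.21) is left out.
- **16.12.** Use the same model at the 42-death look (cut-off still 0.529), for consistency rather than power.
- **Supporting analysis.** Keep the stratified log-rank, with its strata named.
- **Do not** add PS as further log-rank strata. Twelve strata gave about 74-76% in Step 2, and 75.2% against 78.8% for the planned tests when nothing was prognostic.
- **16.51.** Using the same model for PFS is optional.

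**Cost.** No new data and no extra patients. The decision then relies on a Cox model, the hazard-ratio cut-offs in 16.12 to 16.14 (1.022 and 0.797) become approximate labels beside the p-value rule, and the table in 16.151 should be re-simulated under stated PS assumptions. The change must be fixed before outcomes by arm are seen; adding PS afterwards would not be credible as a decision rule.

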6.2 Randomization Procedures

- 6.21 The factors defined in Section 5.0, together with the registering membership, will be used as stratification factors.
- 6.22 After the patient has been registered into the study, the values of the stratification factors will be recorded, and the patient will be assigned to

one of the following treatment groups using the Pocock and Simon [39] dynamic allocation procedure which balances the marginal distributions of the stratification factors between the treatment groups.

- Panitumumab
- Standard Therapy (regorafenib or TAS-102)

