16.14 Decision Rules

Analysis time point	Number of events ¹	Critical p-value		Hazard Ratio	
		Futility	Efficacy	Futility	Efficacy
50%	42	> 0.529	N/A	> 1.022	N/A
100%	83	> 0.15	≤ 0.15	> 0.797	≤ 0.797

¹ Documentation of death

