16.3 Accrual Time and Study Duration

The anticipated accrual rate is approximately 8 patients per month. Therefore, the accrual period for this randomized Phase II study is expected to be around 15 months. The final analysis can begin as soon as the 83rd OS event has occurred; approximately 25 months after the study begins under the alternative hypothesis.

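### Do p ≤ 0.15 and HR ≤ 0.797 create two conflicting rules for the final decision?

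*Combined protocol and SAP*

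**What the plan says.** Section 16.13 sets the trigger: "Efficacy analysis will be conducted when at least 83 death events". It names the deciding statistic: "The stratified log-rank test will be used for decision making except when there are 0 events in any of the strata", in which case the un-stratified version takes over. A p-value above 0.15 means ineffectual, with HR > 0.797 given as the corresponding value. For success the wording is "if the 1-sided p-value ≤ 0.15 (equivalently, HR ≤ 0.797), panitumumab will be considered as promising for future study".

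Section 16.14 puts the cut-offs for both looks in one table. The p-value columns are headed "Critical p-value"; the others carry only the label for the hazard ratio. Section 16.12 gives the interim futility decision to the un-stratified log-rank p-value.

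Section 16.15 sizes the trial on a one-sided 0.15 level with 80% power at HR 0.65, and adds "Stratification factors are defined in section 5.0". A footnote in 16.151 says that "the hypothesis testing is based on the entire survival curve". For allocation, Section 6.21 states "The factors defined in Section 5.0, together with the registering membership, will be used as stratification factors". On timing, Section 16.3 states "The final analysis can begin as soon as the 83rd OS event has occurred".

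**The concern.** The word *equivalently*, together with a table that prints both cut-offs, can be read as two interchangeable rules for one go/no-go decision. They are not interchangeable. A hazard-ratio cut-off matches a p-value cut-off only for a given event count, allocation split and model. Here the event count is a minimum, the test is stratified, and Section 16 names no model for the hazard ratio. No sentence says in so many words which prevails if the two differ. Any conflict would fall at the boundary, where a choice made after seeing the data is hardest to defend. Section 16.13 also does not list its strata, and its switch to the un-stratified test looks unnecessary if the strata are just the two factors in Section 5.0.

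**Working it through.** **1. Reproduce the plan's figure.** Inputs: one-sided 0.15, so z = 1.0364 (16.15); 83 deaths (16.13); 1:1 allocation (16.15). With Var(log HR) = 4/deaths, the cut-off is exp(−2 × 1.0364/√83) = 0.7965, printed as 0.797. The same formula for p = 0.529 at 42 deaths gives 1.0227, against 1.022 in 16.12. Both printed values are normal-approximation translations of the p-value.

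**2. Where the equivalence fails.**
- Rounding: HR 0.797 at 83 deaths gives p = 0.1507, just on the wrong side.
- Event count: by the same formula, the HR matching p = 0.15 is 0.800 at 86 deaths, 0.802 at 88 and 0.804 at 90. At 88 deaths, HR 0.800 gives p = 0.1476.
- Test against estimate: the formula is un-stratified, while the test in 16.13 is stratified.

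**3. How often it matters.** Trials were simulated with 106 patients accrued at 8 per month and exponential survival with a 6.5-month control median. True HR was 1, 0.80 or 0.65. The Cox HR used the same strata as the test. Prevalences of right-sided tumor and prior therapy, and stratum hazard ratios (none, up to 2 and 1.5), are assumptions. Disagreement at exactly 83 deaths:
- 0.4–1.7% with Pocock–Simon allocation (5,000 trials in each of 18 scenarios; prevalences 10%/10%, 20%/20%, 25%/35%);
- 0.7–1.5% with prevalences 25%/40% (4,000 trials per scenario);
- about 0.6–2.4% with simple 1:1 allocation.

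Wherever direction was recorded at 83 deaths, the disagreement was HR ≤ 0.797 with p > 0.15. The p-value is therefore the stricter criterion there. At a true HR of 1 and prevalences 25%/40%, the p-value rule succeeded in 14.7–14.9% of trials and the matched HR rule in 15.7–15.8%.

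A modest overrun does not make this worse. In 12 scenarios of 3,000 trials each, total disagreement was 0.40–1.70% at 83 deaths, 0.27–1.03% at 86, 0.17–0.67% at 88 and 0.10–0.67% at 90. In this setting the stratified Cox value matching p = 0.15 starts below 0.797 at 83 deaths and rises toward it. Trials passing on p but failing on HR were at most 0.2% at 86 deaths and 0.36% at 88 across the runs. At 95 deaths total disagreement was 0.5–1.1%.

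**4. Which criterion decides.** Set side by side, the sections agree. 16.12 and 16.13 each assign the decision to a log-rank test. Both state the conditions as p-values and add the HR as a gloss. 16.14 reserves the label of critical for the p-value and ties its last row to 83 events. 16.15 defines the design by a significance level, and its footnote says that the test concerns the whole curve. No passage assigns the decision to an estimated hazard ratio.

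**5. Design figures under the p-value rule.** A two-look normal simulation (42 then 83 deaths, 1,000,000 replicates) with the futility rule followed gives success in 14.1% of trials at HR 1 (16.151: 14.1%) and 80.3% at HR 0.65 (16.151: 79.4%). Nothing needs recalculating.

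**6. Strata and fallback.** 16.15 points to Section 5.0, so the natural strata are tumor side and prior TAS-102 or regorafenib. A stratum without deaths adds nothing to a stratified log-rank statistic, so with these strata the switch is not needed. It is nevertheless pre-specified and valid. It changed the decision in 1.4–2.8% of simulated trials at prevalences 10%/10%, 0.1–0.3% at 20%/20% and 0% at 25%/35%. The largest gap in the success rate against always stratifying was 15.36% versus 15.10%, or 0.26 points, within simulation noise.

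**The case for a change.** The strongest case for acting is that rewording is free and every conflict sits at the decision boundary. An overrun is also realistic. Survival contacts are three-monthly (Sections 4.0 and 13.2), and 106 − 83 = 23 evaluable patients would remain alive. With exponential survival and no dropout, one contact interval would bring 23 × (1 − 2^(−3/10)) = 4.3 to 23 × (1 − 2^(−3/6.5)) = 6.3 further deaths. And since no model is named, someone could set an un-stratified HR beside the stratified p-value; the two then disagreed in 4–10% of simulated trials at 83 deaths.

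Part of this stands. *Equivalently* is inexact, the HR entries carry no note that they hold only at 42 and 83 deaths, and the HR model is unnamed. But a few extra deaths reduced conflict in the simulations, and 16.3 lets the analysis start at the 83rd death. The un-stratified pairing is proposed nowhere in the plan. Above all, each of these scenarios needs someone to override the named test with an estimate, and the text gives no authority for that. Confining registering membership to allocation and dropping the fallback would be preferences, since the test as written is valid.

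**Conclusion.** This is loose wording, not a second decision rule. The printed 0.797 is a correct approximate translation of p = 0.15 at 83 deaths, and the plan gives the decision to the log-rank p-value. The two cut-offs would differ in roughly 0.4–2.4% of trials at 83 deaths, and generally less often after a small overrun. At 83 deaths the differences run in the direction where the p-value is the more cautious. These rates rest on assumed stratum prevalences and effects, exponential survival, and a Cox model with the same strata as the test. An analyst following Sections 16.12 to 16.15 would use the p-value, take the Section 5.0 factors as strata, and report the hazard ratio as an estimate. The one-sided 0.15 level, the power, the 83 deaths, the 106 evaluable patients and the trial's conclusion would all be unchanged.

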- 6.16 Treatment cannot begin prior to randomization and must begin \leq 7 days after randomization.
- 6.17 Pretreatment tests/procedures (see Section 4.0) must be completed within the guidelines specified on the test schedule.
- 6.18 All required baseline symptoms (see Section 10.52) must be documented and graded.
- 6.19a Treatment on this protocol must commence at an ACCRU institution under the supervision of a medical oncologist.
- 6.19b Study drug is available on site.
- 6.19c Blood draw kit is available on site.

Exclusion: Guardant 360 kit does not need to be on site at the time of registration.

- 6.19d Patient questionnaire booklet is available on site; copies are not acceptable for this submission.

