13.0 Treatment/Follow-up Decision at Evaluation of Patient

- 13.1 Patients who have CR, PR, or SD will continue treatment per protocol for a maximum of 24 cycles. Subsequent treatment is at the discretion of their attending physician.
- 13.2 Patients who develop PD while receiving therapy or choose an alternative therapy will go to the event-monitoring phase and be followed for survival (i.e. event-monitoring phase) every 3 months (± 7 days) for 3 years after randomization (per Section 18.0). Subsequent treatment is at the discretion of their attending physician.
- 13.3 Patients who go off protocol treatment for any reason will go to the event-monitoring phase and be followed for survival (i.e. event monitoring phase) every 3 months (± 7 days) for 3 years after randomization (per Section 18.0). Subsequent treatment is at the discretion of their attending physician.
- 13.4 A patient is deemed *ineligible* if after registration, it is determined that at the time of registration, the patient did not satisfy each and every eligibility criteria for study entry. The patient may continue treatment off-protocol at the discretion of the

physician as long as there are no safety concerns, and the patient was properly registered. The patient will go directly to the event-monitoring phase of the study (or off study, if applicable).

- If the patient received treatment, all data up until the point of confirmation of ineligibility must be submitted. Event monitoring will be required per Section 18.0 of the protocol.
- If the patient never received treatment, on-study material must be submitted. The patient will not be followed for survival.

13.5 A patient is deemed a *major violation*, if protocol requirements regarding treatment in cycle 1 of the initial therapy are severely violated that evaluability for primary end point is questionable. All data up until the point of confirmation of a major violation must be submitted. The patient will go directly to the event-monitoring phase of the study. The patient may continue treatment off-protocol at the discretion of the physician as long as there are no safety concerns, and the patient was properly registered. Event monitoring will be required per Section 18.0 of the protocol.

13.6 A patient is deemed a *cancel* if he/she is removed from the study for any reason before any study treatment is given. On-study material and the Off Treatment Form must be submitted. The patient will not be followed for survival.

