16.11 Primary Endpoint

The primary endpoint for this study is overall survival (OS) which is defined as the time from randomization to death from any cause. Patients who are alive will be censored at the last known alive date.

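### OS is decided in eligible, treated patients only, and randomised patients who are never treated get no survival follow-up, so an all-randomised OS analysis could not be run from the data collected

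*Combined protocol and SAP*

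**What the plan says.** **Endpoint and goal.** Section 16.11 has OS "defined as the time from randomization to death from any cause". Section 16.15 says: "The primary goal is to compare the OS between patients who are randomized to panitumumab and those randomized to standard therapy".

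**Analysis set.** Section 16.13 says: "All eligible patients who sign the consent form, are randomized, and received any protocol treatment are considered evaluable for this endpoint". Section 16.15 is worded to match: "With 53 evaluable patients per arm, we have 80% power". Section 16.12 (interim futility look) names no analysis population. No all-randomised OS analysis appears anywhere, even as a sensitivity analysis.

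**Survival follow-up.**
- Section 13.6, patients removed before any dose (cancels): "On-study material and the Off Treatment Form must be submitted. The patient will not be followed for survival".
- Section 13.4, ineligible patients: "If the patient never received treatment, on-study material must be submitted. The patient will not be followed for survival". Ineligible patients who were treated do go to event monitoring.
- Section 13.3, by contrast: "Patients who go off protocol treatment for any reason will go to the event-monitoring phase and be followed for survival".

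The general event-monitoring lines in Sections 4.0 and 18.1 do not override the specific rules in 13.4 and 13.6.

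**Major violations.** Their status is unclear. Section 16.13 as worded includes them if they are eligible and treated. Section 13.5 calls their evaluability questionable. Section 16.2 counts them among the 14 extra patients, alongside ineligibility, cancellation and other reasons. They are followed for survival.

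**The concern.** Randomisation protects the comparison of everyone randomised. Receiving a first dose happens after assignment. Section 6.16 allows up to 7 days for it, the arms are an IV infusion and oral tablets, no masking is described, and panitumumab is supplied while the control drugs are commercial (19.31). A patient or site could react to the assignment before treatment starts. If the patients who leave differ between arms in number and in prognosis, the treated sets are no longer comparable.

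Many phase II plans use a treated set, but an all-randomised check can usually be added later. Here the protocol tells sites not to collect the survival data that the check needs. OS alone decides whether panitumumab is taken forward. If uneven loss appeared, the sponsor could see it without being able to observe whether it changed the result.

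**Working it through.** **1. Reproduce the plan.** Inputs from 16.12 to 16.15: 83 deaths, one-sided 0.15 (z = 1.0364), 1:1 allocation, HR 0.65, look at 42 deaths with a stop if p > 0.529.
- Critical HR = exp(-2 × 1.0364/√83) = 0.797 (plan 0.797).
- Interim HR = exp(2 × 0.0728/√42) = 1.023 (plan 1.022).
- Power without the look = Φ(0.4308 × √83/2 - 1.0364) = Φ(0.926) = 82.3%. With the look, by the bivariate normal, 80.3% (plan 80%; table 79.4%).
- At HR 1: stop for futility 47.1% (plan 47.7%), success 14.1% (plan 14.1%).

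The design figures are therefore right for the evaluable set, provided there is no selective loss before the first dose.

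**2. Which patients could be restored to the analysis**

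| Group | In the 16.13 set? | Followed for survival? |
|---|---|---|
| Eligible, treated | Yes | Yes |
| Major violation, eligible and treated | Unclear | Yes |
| Ineligible, treated | No | Yes, can be put back |
| Ineligible, never treated | No | No |
| Cancel | No | No |

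Only the last two rows are an unrecoverable gap.

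**3. Possible size, by assumption only.** The documents give no loss by arm and no prognosis for those lost. Simulation: 100,000 trials per case, 60 per arm, uniform accrual over 15 months, exponential OS, control median 6.5 months. A fixed number is lost per arm. The chance of loss changes 2.7-fold (e¹) per SD of a score correlated 0.5 with survival. Two further assumptions: the final log-rank is unstratified (16.13 prefers stratified), and the treated set is also used at the 42-death look (16.12 does not say). Results include the look.

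| Lost, control/panitumumab | Success at HR 1: fitter leave / sicker leave | Power at HR 0.65: fitter / sicker |
|---|---|---|
| 0/0 | 14.1% | 79.8% |
| 3/1 | 16.0% / 12.6% | not run |
| 5/2 | 17.0% / 11.9% | 82.6% / 77.6% |
| 12/2 (extreme) | 25.2% / 7.9% | 88.5% / 70.3% |
| 4/3 | 15.0% / 13.4% | not run |
| 7/7 | 14.4% / 14.2% | not run |
| 5/2 or 12/2, unrelated to prognosis | 14.1% or 14.2% | not run |

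With the correlation varied from 0.3 to 0.7, the 5/2 case gives 15.8-18.3% (fitter leave) or 12.7-11.2% (sicker leave). Analysing all randomised patients gives 14.1% at HR 1 in the 5/2 and 12/2 cases, whichever patients leave.

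**4. Hand check.** Suppose a share q of control is lost, with hazard f times the control average, and panitumumab loses nobody. The apparent HR under the null is exp[(q/(1-q)) ln f]. With q = 4/60 and f = 1/1.5, this is exp(0.0714 × -0.4055) = 0.971. Rejection without the look is 1 - Φ(1.0364 + ln 0.971 × √83/2) = 18.3%; with f = 1.5 it is 12.1%. This simpler method also shows a modest shift in either direction.

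**5. Power cost of an all-randomised test.** If u of 60 panitumumab patients are untreated and have control-arm survival, ln HR shrinks by about (60 - u)/60. For u = 2: Φ(0.4308 × 58/60 × 4.555 - 1.0364) = 80.5%. For u = 7: 75.7%. These are without the look. Simulated with the look: 79.7% with none untreated, 77.8% with 2, 72.8% with 7.

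**6. Time.** At 8 per month and HR 0.65, the 83rd death falls at about month 25.2 among 106 patients (plan about 25) and about month 22.0 among 120.

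**The case against.** The case for the plan is substantial.

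- **It is coherent.** The trial is sized on 53 evaluable patients per arm with 14 extra. A reader might infer that the stated power or boundaries are wrong. They are not; they reproduce.
- **Loss is limited by design.** Drug must be on site (6.19b), treatment must start within 7 days (6.16), and patients who cannot swallow tablets are excluded (3.26). These reduce early loss but do not prevent refusal. Section 18.1 has a form rule for refusal before therapy, which is not evidence of how often it happens.
- **Something is still known about these patients.** Counts, arm and baseline data allow description and tipping-point bounds. A reader might infer that early loss could not be assessed at all; that goes too far. What cannot be had is the observed OS of the never-treated.
- **Excluding ineligible patients need not bias.** Ineligibility is judged on status at registration (13.4). If that is done without regard to arm, the comparison is not distorted. The concern is loss after assignment.
- **The likely effect is modest.** Outside the extreme case it is about 2 to 3 points either way, in a phase II screen at one-sided 0.15. Making the all-randomised set decisive costs about 2 to 7 points of power, which is comparable.

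All of this stands. It limits how much weight the choice of primary set can bear. It does not answer the follow-up gap, which is cheap to close now and may not be recoverable later.

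**Conclusion.** The point holds, as a should-fix. The decisive OS test leaves out randomised patients who are never treated, and the protocol stops collecting their survival. An all-randomised OS analysis, decisive or supportive, therefore could not be run from the planned data.

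Confidence is high on the text and low on the size. The shift at HR 1, from 14.1% to about 16-17% or 12-13%, rests on assumed loss of 3/1 or 5/2 and an assumed link to prognosis. The 25% or 8% figures need all 14 allowance patients to be never treated and split 12/2; Section 16.2 gives that allowance to other reasons too, so 14 of 120 (11.7%) is only an upper guide.

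Two stronger readings are not supported. One is that the result will be biased towards panitumumab: the documents give neither the arm split nor the prognosis of early losses, and the shift could go either way or be nil. The other is that 16.13 excludes major violations: its wording does not, and the sections need reconciling.

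**What to change.** 1. **Essential.** In 13.4 and 13.6, replace the sentences that end survival follow-up with 3-monthly survival follow-up to 3 years from randomisation for every randomised patient, unless consent for all follow-up is withdrawn (18.1 already has a form for that).
2. **Analysis set.** In 16.12 and 16.13, state the population. Analyse OS in all randomised patients by assigned arm, preferably as the decisive analysis, with the eligible-and-treated set as a sensitivity analysis. At the least, pre-specify the all-randomised analysis as a sensitivity analysis. Report loss before the first dose by arm with reasons, and state whether major violations are in the evaluable set.
3. **Power.** If the all-randomised set is decisive, keep 83 deaths and the stated boundaries, and restate power in 16.15: about 78% with 2 untreated panitumumab patients and about 73% with 7, if untreated patients have control-arm survival.

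**Cost.** Protocol wording, and at most 12 contacts per never-treated patient (7 × 12 = 84; 14 × 12 = 168). Stated power is slightly lower only if step 3 applies. The trial is not lengthened. The repair is partial, because patients who withdraw from all follow-up stay lost: if half of the never-treated do so in the 5/2 case, success at HR 1 in the all-randomised analysis is 15.7% or 13.3%, against 17.0% or 11.9% under the current rule.
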